## SUBJECT POPULATION

### Key Inclusion Criteria

- Subjects must be 18 to 70 years of age, inclusive.
- Subjects must have CHB infection documented by:
  - Serum HBsAg-positive at screening and serum HBsAg- or HBV DNA-positive at least 6 months prior to screening;
  - Serum immunoglobulin M (IgM) anti-HBc antibody negative at screening.
- In subjects currently not being treated (Treatment Arms 1-2-3 and 6-7-8):
  - Subjects must not be receiving any CHB treatment at screening, ie,
    - Have never received treatment with HBV antiviral medicines, including NAs or interferon (IFN) products, OR
    - Have not been on treatment with HBV antiviral medicines, including NAs or IFN products, within 6 months prior to baseline (first intake of study drugs), AND
  - Subjects must be HBeAg-positive and have HBV DNA  $\geq 20,000$  IU/mL, OR be HBeAg-negative and have HBV DNA  $\geq 2,000$  IU /mL at screening, AND
  - Subjects must have HBsAg  $> 250$  IU/mL at screening, AND
  - Subjects must have ALT  $>$  upper limit of normal (ULN) and  $\leq 5 \times$  ULN at screening, determined in the central laboratory.

**Note:** If subjects were treated with investigational anti-HBV agents more than 6 months before screening, the sponsor should be contacted to discuss the case. Subjects who have received treatment with a CAM for more than 4 weeks any time prior to screening are excluded.

- In virologically suppressed subjects (Treatment Arms 4-5 and 9-10):
  - Subjects must be virologically suppressed by current NA treatment (ETV or TDF) as defined by HBV DNA <60 IU/mL at screening and at least 6 months prior to screening, AND
  - Subjects must be on the same NA treatment (ETV or TDF) and the same dose for  $\geq 12$  months prior to screening, AND
  - Subjects must have HBsAg >250 IU/mL at screening, AND
  - Subjects must have ALT  $\leq 2$ x ULN at screening.

**Note:** If subjects were treated with investigational anti-HBV agents more than 6 months before screening, the sponsor should be contacted to discuss the case. Subjects who have received treatment with a CAM for more than 4 weeks any time prior to screening are excluded.

**Note:** The current NA treatment can either be a branded product or a locally approved generic alternative (including different salt forms [eg, tenofovir maleate or succinate]). During the study, subjects will receive branded ETV (Baraclude®) or TDF (Viread®) treatment, as applicable.

- Subjects must have:

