### **4.1. Inclusion Criteria**

Each potential subject must satisfy all of the following criteria to be enrolled in the study:

1. Subjects must be 18 (or older legal age of consent as per local requirements) to 70 years

of age, inclusive.

2. Subjects must have a body mass index (weight in kg divided by the square of height in meters) of 18.0 to 35.0 kg/m^2, extremes included.
3. Criterion modified per Amendment 3
  - 3.1. Subjects must have CHB infection documented by:
    - Serum HBsAg-positive at screening and serum HBsAg- or HBV DNA-positive at least 6 months prior to screening;
    - Serum immunoglobulin M (IgM) anti-HBc antibody negative at screening.
4. In subjects currently not being treated (Treatment Arms 1-2-3 and 6-7-8):
  - a. Subjects must not be receiving any CHB treatment at screening, ie,
    - Have never received treatment with HBV antiviral medicines, including NAs or IFN products, OR
    - Have not been on treatment with HBV antiviral medicines, including NAs or IFN products within 6 months prior to baseline (first intake of study drugs), AND
  - b. Subjects must be HBeAg-positive and have HBV DNA  $\geq$ 20,000 IU/mL, OR be HBeAg-negative and have HBV DNA  $\geq$ 2,000 IU /mL at screening, AND
  - c. Subjects must have HBsAg  $>$ 250 IU/mL at screening, AND
  - d. Subjects must have ALT  $>$  upper limit of normal (ULN) and  $\leq$ 5 x ULN at screening, determined in the central laboratory.
- Note:** If subjects were treated with investigational anti-HBV agents more than 6 months before screening, the sponsor should be contacted to discuss the case. Subjects who have received treatment with a CAM for more than 4 weeks any time prior to screening are excluded.
5. Criterion modified per Amendment 3
  - 5.1. In virologically suppressed subjects (Treatment Arms 4-5 and 9-10):
    - a. Subjects must be virologically suppressed by current NA treatment (ETV or TDF) as defined by HBV DNA  $<$ 60 IU/mL at screening and at least 6 months prior to screening, AND
    - b. Subjects must be on the same NA treatment (ETV or TDF) and the same dose for  $\geq$ 12 months prior to screening, AND
    - c. Subjects must have HBsAg  $>$ 250 IU/mL at screening, AND
    - d. Subjects must have ALT  $\leq$ 2x ULN at screening.

**Note:** If subjects were treated with investigational anti-HBV agents more than

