#### 4.2.3 Randomization and stratification factors

The stratification factors found in IWRS are also found in the Electronic Case Report Form (eCRF):

- HBeAg status at screening (positive versus negative)
- HBsAg level at screening
  - HBeAg positive currently not treated subjects
    - Subjects with HBsAg <10000 IU/mL
    - Subjects with HBsAg ≥10000 IU/mL
  - All other
    - Subjects with HBsAg <1000 IU/mL
    - Subjects with HBsAg ≥1000 IU/mL
- Chronic Hepatitis B (CHB)-infected subject population
  - Currently not being treated
  - Virologically suppressed by current NA treatment (ETV or TDF)

The following randomization and stratification factor data will be tabulated:

- A cross-tabulation of the stratification factor HBeAg status and the HBeAg status at baseline/screening by treatment group. The number of subjects and percentages are shown. A totals column and row are included. This table does not have to be presented by subject population and HBeAg status.
- A cross-tabulation of the stratification factor HBsAg status and the HBsAg status at baseline/screening by treatment group. The number of subjects and percentages are shown. A totals column and row are included. This table does not have to be presented by subject population and HBeAg status.
- A tabulation of the stratification factors in the IWRS by treatment group. This table does not have to be presented by subject population and HBeAg status.
- A listing with randomization data (e.g. randomization date, number), stratification factors and randomized / actual treatment will be provided.

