*Status changes from baseline at week 24 and at week 48 (only subjects with treatment extension)* for HBsAg, HBeAg, anti-HBs and anti-HBe status. Only the qualitative result will be considered. Use the selected time point for the week 24 or 48 visit as described in 2.3. The following categories were defined. The categories can be extended when missing values are present. A borderline result will be mapped as negative.

- Positive to Positive
- Negative to Negative
- Negative to Positive
- Positive to Negative

Maximum decrease from baseline is defined as the minimum value for change of baseline for the viral activity parameters HBeAg, HBsAg, HBVRNA, HBVDNA and HBcrAg)

*Biochemical response* or alanine aminotransferase (ALT) normalization from baseline per post-baseline time point is defined for subjects with elevated ALT (ALT>ULN) at baseline as:

- 0 (No) = ALT>ULN
- 1 (Yes) = ALT $\leq$ ULN

*On-treatment failure during week 24 period is defined as:*

- Subject who has at week 4 HBVDNA < 1log10 IU/mL decline from baseline and confirmed by retesting at week 8 visit (apply only for the naïve treatment population)
- Or for subject who experienced viral breakthrough as defined above

*On-treatment failure during week 48 period is defined as:*

- Subject whom after completed week 24 treatment and still on JNJ-56136379 experienced viral breakthrough as defined above

---

- Subject who did not meet the treatment extension criteria at week 24 as defined in the protocol (this should be derived using the criteria below)
  - Completed 24 weeks of treatment
  - HBVDNA levels < 200 IU/mL at week 20
  - No safety concerns during the initial 24 weeks of treatment
- Subject who did not meet the week 40/44 treatment completion criteria as defined in the protocol (this should be derived using the criteria below)
  - Completed 48 weeks of treatment
  - At week 40 and confirmed at week 44
    - Normal ALT levels or elevated ALT levels by investigator opinion
    - HBV DNA <LLOQ
    - HBeAg negative
    - HBsAg < 500 IU/mL
    - $\geq 1$  log10 IU/mL decline in HBsAg from baseline

*Post-treatment failure during follow-up with NA treatment is defined as:*

Subject who completed study treatment at week 24 and did not met the treatment extension criteria or subject who did not met treatment completion criteria at week 48 as defined above or subjects who discontinued study treatment earlier and experienced viral breakthrough as defined above (NA treatment)

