**Table 4: response categories for viral activity parameters**

	Category criteria	Additional info
HBsAg Response	Subject who has achieved a HbsAg level <1000 IU/mL per time point	These proportions will also be included per analysis phase and analysis period. A subject will be included in the numerator if the response category is at least once met within the analysis phase/period.
	Subject who has achieved a HbsAg level <100 IU/mL per time point	
	Subject who has achieved a HbsAg level <10 IU/mL per time point	
	Subject who has achieved a HbsAg level <0.05 IU/mL per time point	
HBV DNA Response	Subject who has achieved a HBV DNA level <1 log10 IU/mL per time point	These proportions will also be included per analysis phase and analysis period. A subject will be included in the numerator if the response category is at least once met within the analysis phase/period.
	Subject who has achieved a HBV DNA level <2 log10 IU/mL per time point	
	Subject who has achieved a HBV DNA level <3 log10 IU/mL per time point	
	Subject who has achieved a HBV DNA level <20 IU/mL per time point	
	Subject who has achieved a HBV DNA level <60 IU/mL per time point	
	Subject who has achieved a HBV DNA level <100 IU/mL per time point	
	Subject who has achieved a HBV DNA level <1000 IU/mL per time point	
	Subject who has achieved a HBV DNA level <2000 IU/mL per time point	
	Subject who has achieved a HBV DNA level <20000 IU/mL per time point	
	Subject who has achieved a HBV DNA level < LLQ for target detected and not detected per time point	
	Subject who has achieved a HBV DNA level < LLQ for target not detected per time point	
	Subject who has achieved a HBV DNA level < LLQ for target detected per time point	
HBV RNA Response	Subject who has achieved a HBV RNA level <100 cp/mL per time point	These proportions will also be included per analysis phase and analysis period. A subject will be included in the numerator if the response category is at least once met within the analysis phase/period.
	Subject who has achieved a HBV RNA level <1000 cp/mL per time point	
	Subject who has achieved a HBV RNA level <2000 cp/mL per time point	
	Subject who has achieved a HBV RNA level <20000 cp/mL per time point	
	Subject who has achieved HBV RNA target not detected per time point	
	Subject who has achieved HBV RNA < LLOQ per time point	
	Subject who has achieved a HBV RNA level <250 cp/mL at week 24	

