**Table 5: Time to event definitions and censored data**

Variables	Definition	Censored data
HBsAg Response	Time to a HBsAg level of $<1000$ IU/mL	Subjects who did not achieve “HBsAg $<xxx$ IU/mL” will be censored at the last HBsAg assessment
	Time to a HBsAg level $<100$ IU/mL	
	Time to a HBsAg level $<10$ IU/mL	
	Time to a HBsAg level $<0.05$ IU/mL	
HBsAg Reduction	Time to a HBsAg reduction of $> 0.3 \log_{10}$ IU/mL	Subjects who did not reduce HBsAg by “ $>xxx \log_{10}$ IU/mL” from baseline will be censored at the last HBsAg assessment
	Time to a HBsAg reduction of $> 0.5 \log_{10}$ IU/mL	
	Time to a HBsAg reduction of $> 1 \log_{10}$ IU/mL	
	Time to a HBsAg reduction of $> 2 \log_{10}$ IU/mL	
	Time to a HBsAg reduction of $> 3 \log_{10}$ IU/mL	
HBsAg Seroclearance (in all subjects)	Time to HBsAg seroclearance as defined in section 5.3.1	Subjects who did not achieve HBsAg seroclearance will be censored at the last HBsAg assessment
HBeAg Seroclearance (in HBeAg-positive subjects only)	Time to HBeAg seroclearance as defined in section 5.3.1	Subjects who did not achieve HBeAg seroclearance will be censored at the last HBeAg assessment
HBeAg Reduction	Time to a HBeAg reduction of $> 0.5 \log_{10}$ IU/mL from baseline	Subjects who did not achieve “HBeAg $<xxx$ IU/mL” from baseline will be censored at the last HBeAg assessment
	Time to a HBeAg reduction of $> 1 \log_{10}$ IU/mL from baseline	
	Time to a HBeAg reduction of $> 2 \log_{10}$ IU/mL from baseline	
HBV virological breakthrough	Time to HBV virological breakthrough as defined in section 5.3.1	Subjects who did not achieve HBV virological breakthrough will be censored at the last HBV DNA assessment during the defined time frame

HBV DNA Response	Time to a HBV DNA level <1 log10 IU/mL	Subjects who did not achieve “HBV DNA <xx log 10” will be censored at the last HBV DNA assessment
	Time to a HBV DNA level <2 log10 IU/mL	
	Time to a HBV DNA level <3 log10 IU/mL	
	Time to a HBV DNA level <100 IU/mL	Subjects who did not achieve “HBV DNA<xxxx IU/mL” will be censored at the last HBV DNA assessment
	Time to a HBV DNA level <1000 IU/mL	
	Time to a HBV DNA level <2000 IU/mL	
	Time to a HBV DNA level <20000 IU/mL	
	Time to HBV DNA < LLQ for target detected and not detected	Subjects who did not achieve HBV DNA<LLQ for both target will be censored at the last HBV DNA assessment

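### SAP Tables 4 and 5 count HBsAg <1,000 IU/mL as a response or event without a baseline condition, so subjects who enter between 250 and 1,000 IU/mL respond at the first visit with no change in HBsAg

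*SAP*

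**What the plan says.** **Entry.** For both populations the protocol states "Subjects must have HBsAg $> 250$ IU/mL at screening" (Synopsis, Key Inclusion Criteria; Section 4.1, criteria 4c and 5.1c). There is no upper limit.

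**Stratification.** SAP Section 4.2.3 lists "Subjects with HBsAg <1000 IU/mL" as a stratum for all subjects except untreated HBeAg-positive ones, whose cut is 10,000 IU/mL.

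**Proportion.** SAP Table 4 defines the category as "Subject who has achieved a HbsAg level <1000 IU/mL per time point". For the summary by phase or period it adds: "A subject will be included in the numerator if the response category is at least once met within the analysis phase/period".

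**Time to event.** SAP Table 5 includes time to HBsAg below 1,000 IU/mL and says only: "Subjects who did not achieve “HBsAg $<xxx$ IU/mL” will be censored at the last HBsAg assessment". It does not mention subjects already below the level at baseline.

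**Contrast.** Elsewhere in SAP Section 5.3 (Parameter Definitions), ALT normalisation "is defined for subjects with elevated ALT (ALT>ULN) at baseline as", and loss of HBsAg or HBeAg requires a positive baseline result.

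**The concern.** Having achieved a level, or the time taken to reach it, has meaning only for someone not already there. The entry rule and the randomisation stratum both show that the plan expects subjects between 250 and 1,000 IU/mL, yet Tables 4 and 5 leave them in the numerator, the denominator and the risk set.

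The category is a protocol secondary endpoint, with <1,000 IU/mL named as an example. If it is reported as written, the rate mixes where subjects started with what happened on treatment. A reader would take part of the entry distribution for response, and a true difference between arms would look smaller than it is among subjects who could convert.

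HBV DNA has the same problem in virologically suppressed subjects. They must have HBV DNA <60 IU/mL to enter, so the Table 4 categories from <60 IU/mL upwards (including <2 and <3 log10) are close to automatic for them.

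**Working it through.** The plan gives no figure that depends on this rule, so there is nothing to reproduce. The check has four steps.

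**1. How far HBsAg can rise and still count.** Entry is above 250 IU/mL and the threshold is 1,000 IU/mL. log10(1000/250) = 0.60. A subject entering just above 250 IU/mL could rise by almost 0.60 log10 and still meet the category.

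**2. How many subjects fall where the <1,000 IU/mL stratum applies.** Each part plans 70 untreated and 40 suppressed subjects, with about 40% of the untreated HBeAg-positive (Protocol Section 3.1). Untreated HBeAg-negative: 0.60 × 70 = 42. Adding 40 suppressed gives 82 of 110, about 75%.

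**3. Effect on the reported proportion.** Let q be the share below 1,000 IU/mL at entry and r the true rate of newly reaching the level among the rest. Assume that q is equal in both arms and that subjects already below stay below. Then:

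- reported rate = q + (1 − q) × r
- reported difference = (1 − q) × (r_active − r_control)

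The documents do not give q; 10% to 40% is assumed. The rates r = 5% on control and 20% on active (true difference 15 points) are also assumed. The 10/30 split is the planned size of a placebo+NA and a combination arm.

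| q | Reported rate if r = 0 | Reported, control vs active | Difference | Already below, of 10/30 | At risk, of 10/30 |
|---|---|---|---|---|---|
| 10% | 10% | 14.5% vs 28.0% | 13.5 points | 1/3 | 9/27 |
| 20% | 20% | 24.0% vs 36.0% | 12.0 points | 2/6 | 8/24 |
| 30% | 30% | 33.5% vs 44.0% | 10.5 points | 3/9 | 7/21 |
| 40% | 40% | 43.0% vs 52.0% | 9.0 points | 4/12 | 6/18 |

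On active treatment, the share of reported responders who already met the category at entry is q divided by the reported rate: 0.10/0.28 = 36% up to 0.40/0.52 = 77%.

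The rule by phase goes further. SAP Table 2 places the pre-dose baseline record inside the treatment phase, and Section 5.3 excludes that record only when defining viral breakthrough. Read literally, a subject at 900 IU/mL on Day 1 who then stays above 1,000 IU/mL is still a treatment-phase responder.

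**4. HBV DNA in the pooled display.** SAP Section 2.6 also calls for tables over the whole study population. By the planned numbers in each part, suppressed subjects make up 10 of 20 on placebo+NA, 30 of 60 on combination and 0 of 30 on monotherapy. For HBV DNA thresholds of 60 IU/mL and above, the two NA-containing columns therefore start near 50% and the monotherapy column does not. Randomisation cannot correct this, because monotherapy is given only to untreated subjects.

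**The case against.** The best defence is that this is a level category by design. The protocol pairs absolute levels with reductions from baseline, and the reductions isolate change. ALT normalisation and seroclearance are transitions by meaning; a level is not. The study is exploratory, with no formal testing. SAP Section 5.3 tabulates the absolute-level categories but leaves them off its list of endpoints for differences and confidence intervals; the HBsAg entries there are seroclearance, seroconversion and reduction. Baseline HBsAg group is tabulated by arm and is a listed subgroup.

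Much of this stands, and it rules out several stronger readings.

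- *A reader might infer that an inactive drug would look better than placebo+NA.* The documents do not support that for HBsAg. Concurrent placebo+NA has the same floor, and stratification at 1,000 IU/mL keeps the entry share similar between arms for about 75% of subjects.
- *A reader might infer that a Kaplan-Meier curve or log-rank test is distorted.* The SAP calculates the time-to-event variables but specifies no such output. The gap lies in the definition.
- *A reader might infer a large chance imbalance in untreated HBeAg-positive subjects, who are not stratified at 1,000 IU/mL.* With 4 versus 12 subjects and an entry share of 25%, the SD of the difference is √(0.25 × 0.75 × (1/4 + 1/12)) = 25 points. But nothing supports 25% in this group: Protocol Table 1 describes its HBsAg as high or high/intermediate, and its stratum is cut at 10,000 IU/mL. At 5% the same formula gives about 13 points. Balance is unprotected there, but its size is unknown.

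The defence does not remove the gap. The SAP labels the category a response and assigns it an event time, neither of which fits a subject already below the level. The baseline subgroup applies only where judged appropriate, is not tied to Tables 4 and 5, and is absent from the default split in Section 2.6.

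**Conclusion.** The point holds as a defect of definition in a descriptive secondary display. As written, entrants below 1,000 IU/mL are responders, with an event at the first visit, without any fall in HBsAg. The absolute rate is inflated by up to the full entry share, and any informal contrast between arms is multiplied by (1 − q). For q between 10% and 40%, that means 10% to 40% reported with no true response, and 13.5 to 9 points reported for a true 15.

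These sizes rest on assumed values of q and r and on subjects already below staying below. The direction does not depend on them.

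A reader might extend the point to the main HBsAg results, and the documents do not support that. Change from baseline at Week 24 and the reduction categories are measured against each subject's own baseline. The <100, <10 and <0.05 IU/mL categories lie below the entry limit.

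**What to change.** - **Table 5:** restrict the risk set for time to HBsAg <1,000 IU/mL to subjects with baseline HBsAg of at least 1,000 IU/mL.
- **Table 4:** report the <1,000 IU/mL response proportion among subjects with baseline of at least 1,000 IU/mL, counting post-baseline records only. Keep the all-subject proportion that the protocol defines as a descriptive display of level.
- **HBV DNA thresholds of 60 IU/mL and above, including <2 and <3 log10:** do not present these as response or time to event in virologically suppressed subjects or in the pooled whole-population table. Show them as maintenance of suppression.

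The cost is SAP wording and a programming filter; study conduct does not change. The drawback is smaller denominators: a 10/30 comparison becomes 9/27 at q = 10% and 6/18 at q = 40%. Within HBeAg subgroups, where Protocol Table 7 expects only 3 to 7 placebo+NA subjects, some cells may be too small to report as more than counts.

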Treatment with JNJ-56136379 may lead to emergence of viral variants with reduced susceptibility or resistance to JNJ-56136379. Based on pre-clinical data, these variants remain susceptible to TDF and ETV but might affect treatment options with CAMs in the future.

As of 6 February 2019, virological breakthrough, as defined by the protocol (ie, confirmed on-treatment HBV DNA increase  $>1 \log_{10}$  from nadir level or confirmed on-treatment HBV DNA level  $>200$  IU/mL in subjects who had HBV DNA level below the LLOQ of the HBV DNA assay), was observed in 5 out of the 28 subjects on JNJ-56136379 75 mg monotherapy. In addition, there were 2 subjects who met the virological breakthrough threshold but, due to the change of treatment, the virological breakthrough could not be confirmed. The virological breakthrough in these subjects is expected to be associated with viral resistance to JNJ-56136379. An HBV DNA decline was observed in these subjects upon initiation of NA treatment confirming pre-clinical data showing that viral variants resistant to JNJ-56136379 remain susceptible to NA treatment.

Given the virological breakthroughs observed in the JNJ-56136379 75 mg monotherapy arm (Treatment Arm 1), this treatment arm was discontinued early per Protocol Amendment 4. All subjects were to stop further dosing with JNJ-56136379 75 mg, start treatment with NA, and enter the post-treatment follow-up phase (Schedule 1).

In addition, per Protocol Amendment 4, the duration of treatment with JNJ-56136379 250 mg monotherapy has been limited to a maximum of 24 weeks (see Section 6.1). As an additional precautionary measure to safeguard the subjects, a stringent futility rule has been implemented in the JNJ-56136379 250 mg monotherapy arm (see Section 6.2).

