10. The subject has a QTcF prolongation (defined as a QTcF value of  $>500$  ms, or an increase from baseline of  $>60$  ms) at any given time point (confirmed by repeat ECG).
11. The subject has at Week 4  $<1 \log_{10}$  IU/mL decline in HBV DNA from baseline, confirmed by retesting at the Week 8 visit (treatment-naïve only).
12. The subject has confirmed HBV virological breakthrough (ie, confirmed on-treatment HBV DNA increase by  $>1 \log_{10}$  IU/mL from nadir level or confirmed on-treatment HBV DNA level  $>200$  IU/mL in subjects who had HBV DNA level  $<$  LLOQ of the HBV DNA assay).
13. The subject requires treatment with any of the disallowed medications listed in Section 8.

Retesting for confirmation of the above-mentioned abnormal safety parameters (ie, not applicable to criteria 11 and 12 listed above) should take place within 72 hours after the initial results become available and may require an unscheduled visit.

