**Table 1: Construction of phases**

Analysis phase	Analysis Period	Start date	End date
Screening (phase 1)		The date of signing the informed consent	1 day before the first study agent intake
Treatment (phase 2)	Initial Treatment	Date of first study agent intake	- If not included in the treatment extension°: Date of last study agent intake + 5 days*

Analysis phase	Analysis Period	Start date	End date
	(period 1)		- If included in the treatment extension o : Date of Week 24 study agent intake+5 days #
	Treatment Extension (period 2)	End of the initial treatment period + 1 day	Date of last study agent intake + 5 days*
Follow-up (phase 3)		End of the treatment phase +1 day	Trial termination date (date of last contact) or cut-off date for an interim analysis, whichever comes first

o depending on the answer in the FA dataset: FAOBJ = " WILL THE SUBJECT CONTINUE TREATMENT IN TREATMENT EXTENSION PHASE?" and whether actually treatment was extended in the EX dataset.

\* or study termination date (date of last contact) or cut-off date for an interim analysis, whichever comes first.

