**Table 2: Construction of Analysis Time point and Visit Window**

Analysis phase	Analysis period	Target daya	Analysis time point (numeric version)	Analysis time point	Time interval (days)b
Screening		$-\infty$	-1	Screening	<0
Treatment	Initial Treatment	1	0	Baseline	Pre-dose
		7	1	Week 1	[2,11]
		14	2	Week 2	[12,21]
		28	4	Week 4	[22,42]
		56	8	Week 8	[43,70]
		84	12	Week 12	[71, 98]
		112	16	Week 16	[99, 126]
		140	20	Week 20	[127, 154]
		168	24	Week 24	[155, 182]
	Treatment Extension	196	28	Week 28	[183, 210]
		224	32	Week 32	[211, 238]

		252	36	Week 36	[239, 266]
		280	40	Week 40	[267, 294]
		308	44	Week 44	[295, 322]
		336	48	Week 48	[323, $+\infty$ ]
	last visit in treatment phase		49*	EOT	
Follow-up		9	50	Follow-up Week 2	[1,16]
		23	52	Follow-up Week 4	[17,30]
		37	54	Follow-up Week 6	[31,44]
		51	56	Follow-up Week 8	[45,65]
		79	60	Follow-up Week 12	[66,93]
		107	64	Follow-up Week 16	[94,121]
		135	68	Follow-up Week 20	[122,149]
		163	72	Follow-up Week 24	[150,191]
		219	80	Follow-up Week 32	[192,247]
		275	88	Follow-up Week 40	[248,303]
		331	96	Follow-up Week 48	[304, $+\infty$ ]
Overall		last visit in the study	999*	EOS	

a Target day in follow-up phase equals target day in the protocol minus 5 days.

b The reference day of the Treatment and Screening phase is the day of the first study agent intake (= day 1 in Treatment phase). The reference day of the Follow-up phase is the first day of the follow-up phase.

\*End of treatment and End of study visit (last available data at the end of the study) will be derived

The number of days in the treatment phase (ADY) will be defined as:

$ADY = \text{visit date} - \text{date of first study drug intake} + 1$  for visits on or after the day of first study drug intake

$ADY = \text{visit date} - \text{date of first study drug intake}$  for visits before the day of first study drug intake

The number of days in the follow-up phase (ADY) will be defined as:

$ADY = \text{visit date} - \text{start date of the follow-up phase} + 1$

All visits (regardless the investigated parameter) will be allocated within each phase/period to analysis time points based on the number of days in phase (ADY)

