## **2.4. Missing and Partial data**

In general, missing data and partial dates will not be imputed and will be treated as missing. Only partially missing diagnosis and infection dates will be temporarily imputed to calculate the duration of infection and the time since diagnosis (see section 4.2.3). The original, non-imputed, dates will be listed.

To calculate the duration of infection or duration of diagnosis, if the reported date is partially missing, the imputation rules below is to be considered:

- Impute with the first day of the month if only day is missing
- Impute with January 1st if only the year is available
- Leave missing if completely missing

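### Per-visit HBV DNA response (SAP Table 4) has no denominator and no rule for subjects stopped for virologic failure, so an observed-case rate at <20 IU/mL would be too high

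*SAP*

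**What the plan says.** Protocol 2.1 makes the proportion of subjects in each HBV DNA response subcategory a secondary endpoint and leaves the detail to the SAP. SAP Table 4 supplies it in rows such as "Subject who has achieved a HBV DNA level <20 IU/mL per time point". The table states no denominator and does not say how a subject who has stopped study agent is classified at later visits.

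Three other SAP rules decide what data such a subject has:
- SAP 2.4: "In general, missing data and partial dates will not be imputed and will be treated as missing".
- SAP 2.3, Table 1: without the extension, the treatment phase ends at "Date of last study agent intake + 5 days".
- SAP 2.3, text under Table 2: visits "will be allocated within each phase/period to analysis time points based on the number of days in phase (ADY").

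Protocol 10.2 requires JNJ-56136379 to be stopped on HBV DNA grounds in two cases. Criterion 12: "The subject has confirmed HBV virological breakthrough". Criterion 11: a fall of less than 1 log10 at Week 4, "confirmed by retesting at the Week 8 visit (treatment-naïve only").

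Protocol 1.3.4 reports that, as of 6 February 2019, breakthrough "was observed in 5 out of the 28 subjects on JNJ-56136379 75 mg monotherapy". Two further subjects crossed the threshold but could not be confirmed because their treatment had been changed. Protocol Amendment 4 then stopped dosing in the whole of that arm (Arm 1).

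SAP 5.3 already identifies these failures elsewhere. On-treatment failure in the 24-week period is built from the same two triggers, and breakthrough status, once reached, is kept at all later time points. Neither is tied to Table 4.

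**The concern.** The values that go missing after such a stop are not missing at random. The stop is caused by the marker being tabulated, and the subject's status as a virologic failure is known, so no model or imputation is needed to classify them. If they simply lack a value at Week 20 or Week 24, a rate based on available values describes only those who had not yet failed. A subject could be a breakthrough at Week 24 in one table and absent from Week 24 response in another.

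At stake is the size of a protocol secondary endpoint, and any reading of the per-visit rates as the share of treated subjects who reach and hold suppression on the assigned regimen.

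**Working it through.** The documents give no expected HBV DNA response rate and no power figure for it (protocol Table 7 concerns HBsAg), so there is no planned figure to reproduce. The check has three steps.

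**1. Does a stopped subject have a Week 24 record?** Let L be the day of last intake. The treatment phase ends on Day L + 5 and follow-up starts on Day L + 6, so calendar Day 168 is follow-up day 168 − (L + 6) + 1 = 163 − L. Using the Table 2 windows:
- L = 56: follow-up day 107, Follow-up Week 16
- L = 84: follow-up day 79, Follow-up Week 12
- L = 112: follow-up day 51, Follow-up Week 8
- L = 140: follow-up day 23, Follow-up Week 4

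The Week 24 window opens on Day 155, so a record there needs L + 5 ≥ 155, that is L ≥ 150. Anyone last dosed on Day 149 or earlier has none, and SAP 2.4 does not fill the gap.

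**2. In which direction does leaving them out push the rate?**
- Breakthrough: SAP 5.1 sets target-not-detected values to 5 IU/mL, the lowest possible nadir. A rise of more than 1 log10 from there means HBV DNA above 50 IU/mL; the other limb of the definition needs more than 200 IU/mL.
- Non-response: the lowest entry level is 2,000 IU/mL (protocol 4.1, taking screening as baseline). A fall of less than 1 log10 leaves more than 200 IU/mL.

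Both kinds of failure are therefore above 20 IU/mL when stopped, and leaving them out can only raise the rate at <20 IU/mL or a stricter cut-off. At looser cut-offs the sign is not fixed: a subject with breakthrough at just over 200 IU/mL still meets <1000, <2000 and <20000 IU/mL.

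**3. How large is it in 75 mg monotherapy?** Let N = 28 and let k subjects be stopped for failure before the visit, with nobody else missing. The observed-case rate is r/(N − k), against r/N when failures count as non-responders, so the inflation factor is N/(N − k).
- k = 5 (confirmed breakthroughs, 5/28 = 17.9%): 28/23 = 1.22
- k = 7 (adding the two unconfirmed): 28/21 = 1.33

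The responder count r is not in the documents. Over assumed values with k = 5:

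| r | observed-case r/23 | failures counted r/28 | gap, points |
|---|---|---|---|
| 7 | 30.4% | 25.0% | 5.4 |
| 12 | 52.2% | 42.9% | 9.3 |
| 15 | 65.2% | 53.6% | 11.6 |
| 18 | 78.3% | 64.3% | 14.0 |
| 22 | 95.7% | 78.6% | 17.1 |

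With k = 7 the gap runs from 7.1 points (6/21 against 6/28) to 23.8 points (20/21 against 20/28).

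**The case against.** The best reply is that the SAP nowhere says these subjects leave the denominator. Efficacy is analysed in the ITT population, and where the SAP narrows a denominator it says so (viral relapse, breakthrough during NA follow-up, sequencing). On that reading a stopped subject already counts as a non-responder and there is no inflation. This stands as far as it goes: exclusion is an inference, not a written rule. It does not settle the matter. A plain ITT denominator in Arm 1 would also count as non-responders those subjects who stopped only because the sponsor closed the arm. One reading overstates the rate and the other understates it, so a rule is needed either way.

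The failures are also visible elsewhere: the cumulative breakthrough proportion, the EOT time point (which keeps the last on-treatment value), and listings of subjects with breakthrough. That is real but partial mitigation. EOT mixes treatment durations, and the per-period version of Table 4 counts anyone who responded at least once, including those who later broke through. The study is exploratory, and HBV DNA level response is not on the SAP 5.3 list of proportions whose differences may be calculated.

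Three stronger readings are tempting but unsupported:
- A reader might infer inflation by a third. That needs the two unconfirmed cases to be counted as failures; they were not stopped as confirmed breakthroughs under criterion 12.
- A reader might infer that the bias is largest in monotherapy. Only the 75 mg arm has reported counts. Amendment 4 records no breakthrough to date in 250 mg monotherapy, and no counts are given for the combination or placebo+NA arms.
- A reader might infer that every Table 4 cut-off is inflated. Step 2 shows this only at <20 IU/mL and stricter.

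**Conclusion.** The gap is real, and narrower than a general charge of inflated response rates. As written, the phase and missing-data rules leave subjects stopped for breakthrough or confirmed non-response without a value at later treatment visits, and nothing links their known failure to Table 4. An observed-case rate at <20 IU/mL or stricter is then biased upward, measured against a rate that counts virologic failure as non-response.

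For 75 mg monotherapy the supported factor is 1.22, or about 5 to 17 percentage points over the assumed responder counts. This holds if all five confirmed cases stopped before the visit and no one else is missing. Neither condition can be checked, because the documents do not give breakthrough times or the effect of the Arm 1 closure by study week. The actual denominator at a given visit may therefore be neither 23 nor 28. No ranking of arms follows. The point merits a change to the SAP because the remedy is specific and cheap.

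**What to change.** In SAP 5.3, for on-treatment HBV DNA response at <20 IU/mL (LLOQ) and stricter cut-offs:
- Use ITT subjects as the denominator.
- Count as a non-responder, at every later planned visit to Week 24 (Week 48 for extension subjects), anyone who meets the SAP's existing on-treatment failure triggers of breakthrough or confirmed Week 4/8 non-response and stopped study agent for it. Use only these triggers: the SAP's Week 48 failure definition also includes missing the extension or completion criteria.
- Show subjects stopped only because Arm 1 was closed in a separate row, not as failures. State where the two unconfirmed cases go, since the SAP's meaning of confirmed also accepts the last on-treatment time point.
- Leave cut-offs above LLOQ as observed-case, and keep the observed-case table at LLOQ as a sensitivity display.

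The cost is a paragraph of SAP text and one extra derivation on flags the SAP already defines. The downside is somewhat lower reported response rates.
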